Body temperature is one of the most frequently studied physiological variables in hospitalized patients. The normal temperature value is around 36.7°C, with significant variability ranging from 35.3 to 37.7°C among different individuals or within the same person throughout the day. The definition of fever is established by a consensus reached by the American College of Critical Care Medicine and the IDSA, placing it at a central temperature of 38.3°C (1), where central temperature refers to the temperature of internal organs. This thermal elevation is typically found in approximately 50% of critical patients (2) and is not only clearly associated with infectious processes but can also be observed in various other conditions such as autoimmune diseases, oncological conditions, bleeding, inflammatory reactions, after surgical procedures, or drug-induced (3).

There are multiple methods for temperature measurement in Intensive Care Units (ICUs), with the most common being peripheral temperature measurement every eight hours using contact thermometers in the axilla(4). In patients with sustained fever or those undergoing therapeutic hypothermia, continuous monitoring of central temperature through rectal, tympanic, vesical, or esophageal methods can be performed (5). However, it is considered a more invasive measure, and its use is limited mainly due to technical difficulties, higher economic costs, and potential serious complications (6, 7).

Thermal monitoring in critical patients is essential. Many critical patients with fever will receive antibiotic treatment, even in the absence of evidence of infection, as early initiation of this treatment in septic patients clearly improves survival (8, 9).

The wide variability of temperature between individuals, circadian changes, different methods of temperature measurement, the influence of medications, and deficiencies in measurement methods make defining fever with a single temperature value impractical (10) Therefore, other patient variables should also be considered before establishing the presence of fever. One of these variables is the thermal curve, or the evolution of temperature throughout the day, which can be sustained or in peaks and may or may not respond to antipyretics, antibiotics, or other temperature control methods. Studying a patient's thermal curve is useful even before reaching definitive fever values (11).

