Primary Objective:

To assess the concordance of temperature obtained continuously by a thermal imaging camera with that obtained by an axillary contact thermometer.

Secondary Objectives:

1. To describe the sociodemographic (age and gender) and clinical characteristics (HTN, DM, DL, reason for ICU admission, SAPS3) of the study population.
2. To study the diagnostic test validity of the thermal imaging camera for fever and hypothermia. Fever is defined as an axillary temperature of $\geq 37.5^{\circ}\text{C}$, and hypothermia is defined as an axillary temperature $< 34.2^{\circ}\text{C}$.
3. To determine the time difference until fever detection between the SF-HANDHELD-80TA05 thermal imaging camera or similar, and temperature measurement through the usual nursing practice following standard protocols in critical patients.
4. To describe the continuous thermal curve patterns taken by the thermal imaging camera in patients with the following pathologies: altered level of consciousness, acute coronary syndrome, cardiac rhythm disturbances, cardiac arrest, heart failure cardiogenic shock, hypovolemic shock, sepsis/septic shock, shock of other etiology, respiratory failure, renal failure, metabolic disorders, intoxications, trauma, postoperative monitoring and surveillance, non-surgical procedure monitoring and surveillance, and others. Thermal curves will be obtained in at least 20 patients per pathology.

5. To describe the continuous thermal curve patterns taken by the thermal imaging camera in patients with infectious complications in two cases: patients with infection upon admission and patients who develop infection during admission. Thermal curves will be obtained in at least 20 patients in each case.
6. To determine the adequacy of regional thermal measurement by reviewing the complete thermal image obtained by the SF-HANDHELD-80TA05 or similar camera

Materials and Methods

Design:

This is a single-center, observational, descriptive, longitudinal, and prospective study to investigate the concordance between temperatures obtained by the thermal imaging camera and axillary temperatures.

Scope and Study Population:

The study will be conducted on all patients admitted to the ICU rooms at HLA Moncloa University Hospital equipped with an infrared camera for continuous measurement of skin temperature.

Inclusion Criteria:

- Patients admitted to the ICU in a room with a thermal imaging camera
- Aged 18 years and above

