- Patients who provide voluntary consent to participate in the study (Annex 2). If the participant is not in full physical or intellectual capacity to provide their signature in the informed consent, the responsible investigator will seek consent from their direct family member or the legally designated person to make decisions on their behalf regarding health matters. This measure is adopted to ensure the participant's rights are respected and the integrity of the consent process is maintained, even in situations where their decision-making capacity may be compromised.

Exclusion Criteria:

Patients from whom information from the thermal imaging camera cannot be obtained due to technical reasons.

Sample Size:

To determine the degree of concordance between the temperature recorded by the thermal camera and axillary temperature, a minimum of 224 pairs of data (224 temperature records by thermal camera vs. 224 axillary temperature records) will be required to estimate an Intraclass

Correlation Coefficient (expected to be 0.8 or higher) with an estimation error of +- 0.05 points, a confidence level of 95%, and anticipating a 10% loss.

Data Collection:

Temperature measurements will be autonomously recorded by the SF-HANDHELD-80TA05 thermal imaging camera, or another with similar characteristics, which provides temperature values every second, thermal images, bed number, date, and time.

The rest of the variables needed for the study will be manually collected by the researchers or through the clinical information system (CIS) "Innovian" and included in a study-dedicated database hosted on the hospital intranet.

Finally, all data will be collected in a pseudonymized manner. For this purpose, two databases will be constructed. One will contain personal data associated with a code (one for each patient), which will be safeguarded by the investigator. The second database will contain the associated clinical data. In the case of images generated by thermal cameras, these will also be pseudonymized, generating images with the aforementioned association code. These coded images will be sent to the Computing Center of the European University of Madrid for the creation of temperature patterns (secondary objectives 4 and 5) and for the adequacy of regional thermal measurement (secondary objective 6).

Standard Practice in Peripheral Temperature Measurement in Our Unit

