The standard practice for peripheral temperature measurement in the ICU at HLA Moncloa University Hospital is not formally documented but adheres to recommendations for monitoring temperature in critically ill patients. Peripheral temperature is obtained using a contact thermometer in the axilla every 8 hours or whenever thermal disturbances are suspected by healthcare personnel (both medical and nursing staff).

Axillary temperature measurement through standard practice will be repeated every 8 hours and collected in triplicate to establish an average used for assessing concordance at that point and so forth until reaching the 224 measurements needed to complete the primary objective of the study. If, during the 8-hour collection, there is a difference of more than 15% between the first 3 measurements, a fourth measurement will be taken, and only the average of the three most similar measurements will be used for concordance. If all four measurements are different, a fifth measurement will be taken, and so on until three measurements considered similar are obtained.

Definitions of Thermal Disturbances and Infectious Complications:

- Fever: Defined as a central temperature (rectal, esophageal, vesical, or tympanic) $\geq 38.3^{\circ}\text{C}$. Peripheral temperature (cutaneous or axillary) is 0.6 to 1°C lower than central temperature; therefore, for this study, we will consider a peripheral temperature $\geq 37.5^{\circ}\text{C}$ as a fever.
- Hypothermia: Defined as a central temperature $< 35^{\circ}\text{C}$ or peripheral temperature $< 34.2^{\circ}\text{C}$.
- Infectious Complications: Will include both patients admitted to the ICU due to an infection (pre-admission infection) and patients who develop an infection during their stay in the ICU (infection during admission). Identification and diagnosis of either type of infection will be

carried out by the attending physician following established clinical practice recommendations and guidelines in each specific case. The task of the researchers will be limited to reviewing the patient's medical history and collecting data.

Temporal Differences in Fever Detection:

The time of fever detection will be identified for each measurement method (standard practice vs. thermal imaging camera), and the temporal difference in minutes between them will be determined.

Creation of Temperature Patterns:

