Continuous temperature data (every second) offered by thermal cameras will be represented by 24-hour thermal curves and classified automatically based on patterns and patient characteristics using unsupervised machine learning algorithms such as clustering. For this purpose, the data will be physically and securely sent to the Computing Center of the European University of Madrid.

Adequacy of Regional Thermal Measurement:

Thermal cameras SF-HANDHELD-80TA05 or similar perform a scan across the entire thermal image to extract the point of maximum temperature found. It is deemed necessary for the study to visually check the thermal images obtained to verify the adequacy of temperature measurement—ensuring that the temperature is being obtained from the patient and not from any other high-temperature element, such as healthcare personnel or electronic devices (mobile phones, respirators, pumps, etc.). A direct visual check of a sample of thermal images will be performed by the researchers, and all thermal images will be physically and securely sent to the Computing Center of the European University of Madrid for automatic classification using convolutional image recognition algorithms (machine learning) to identify whether the temperature is obtained from the patient or any other element.

Interventions and Procedures:

1. All patients admitted to the ICU in a room with a thermal imaging camera will be considered potential candidates for inclusion in the study and will be verbally informed and provided with patient information sheets about the study, requesting their signature on the informed consent form for participation.
2. If they agree to participate, compliance with inclusion and exclusion criteria will be confirmed.
3. Patients will receive treatments according to the center's usual clinical practice and the criteria of their attending physician based on the patient's characteristics in each specific case.
4. The thermal imaging camera will automatically record temperature readings every second and capture a thermal image. The information will be recorded in real-time on

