- Time to Fever Development

Statistical Analysis Plan

The degree of agreement between temperature measurements recorded with the thermal camera and measurements taken with the axillary contact thermometer will be assessed, as these are quantitative variables, through the intraclass correlation coefficient. Qualitative variables will be summarized based on absolute and relative frequency (n and %), while normally distributed quantitative variables will be described using mean \pm standard deviation (SD), or if not normally distributed, using median and interquartile range. Normality will be determined using the Kolmogorov-Smirnov test.

The validity of the thermal camera as a diagnostic test for fever and hypothermia will be calculated based on sensitivity and specificity, as well as Positive Predictive Value (PPV) and Negative Predictive Value (NPV). Considering fever is defined as $\geq 37.5^{\circ}\text{C}$ in axillary temperature, and hypothermia as $<34.2^{\circ}\text{C}$ in axillary temperature.

Limitations

This is a single-center study; other units may have different protocols for monitoring, managing, and treating fever, or admit patients with different baseline characteristics than those in this sample, so the conclusions of this study may not be applicable to other services.

Ethical and Legal Aspects

This study will be conducted in accordance with current legislation. All participating researchers will adhere to strict confidentiality in accessing, collecting, and processing data in

the databases, and commit to strict compliance with relevant laws: Law 41/2002, of November 14, which regulates patient autonomy and rights and obligations regarding clinical information and documentation, Organic Law 3/2018, on the protection of personal data and the guarantee of digital rights, and Regulation (EU) 2016/679 of the European Parliament and of the Council of April 27, 2016, on the protection of individuals concerning the processing of personal data and on the free movement of such data, repealing Directive 95/46/EC (General Data Protection Regulation).

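### The single ICC over repeated 8-hourly pairs mixes between-patient and within-patient agreement, so it cannot show whether the camera follows a patient's own temperature changes

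*Protocol*

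**What the plan says.** The primary objective is "To assess the concordance of temperature obtained continuously by a thermal imaging camera with that obtained by an axillary contact thermometer". Under Standard Practice in Peripheral Temperature Measurement in Our Unit, the axillary reading "will be repeated every 8 hours and collected in triplicate to establish an average used for assessing concordance at that point and so forth", until the target of 224 is met. The Sample Size section counts pairs, not patients: "a minimum of 224 pairs of data (224 temperature records by thermal camera vs. 224 axillary temperature records) will be required". The target is an intraclass "Correlation Coefficient (expected to be 0.8 or higher) with an estimation error of +- 0.05 points, a confidence level of 95" per cent, "anticipating a 10% loss".

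For the analysis, the Statistical Analysis Plan section states that agreement between the camera and the "axillary contact thermometer will be assessed, as these are quantitative variables, through the intraclass correlation coefficient". It names no other agreement statistic. The protocol gives no number of patients, no cap on pairs per patient, no patient effect and no split between and within patients.

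The protocol also shows that change within a patient matters. The background says that studying a patient's "thermal curve is useful even before reaching definitive fever values". Under Creation of Temperature Patterns, the per-second camera data "will be represented by 24-hour thermal curves". Objective 3 compares the time to fever detection between the two methods. Objectives 4 and 5 describe thermal curves.

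**The concern.** With several pairs per patient, one ICC over all pairs adds two sources of agreement. Between patients, it rewards a camera that reads higher in patients who are warmer on average. Within a patient, it rewards a camera that rises and falls with the axilla. The two are weighted by the variance that each happens to contribute, and the result does not show which one produced it.

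The objectives do not use the two parts equally. The shape of a thermal curve (Objectives 4 and 5) is mainly a within-patient matter. Fever is a fixed axillary threshold of 37.5°C, so Objectives 2 and 3 need the right level in each patient, and the timing in Objective 3 needs tracking as well. A respectable overall ICC could therefore be read as support for the curve work without showing that the camera follows a patient.

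**Working it through.** **1. The plan's own figure.** Bonett's precision formula for an ICC with k = 2 methods, r = 0.80, full width w = 0.10 and z = 1.96 is

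n = 8z²(1−r)²(1+(k−1)r)² / [k(k−1)w²] + 1

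This gives 199.14 + 1 = 200.14, so 201 pairs. Allowing for 10% loss, 201/0.9 = 223.3, so 224. The stated number is reproduced. The formula treats pairs as independent and contains no patient level.

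**2. A camera with no within-patient tracking.** Write the axillary reading as b + w (patient level plus within-patient change) and the camera as b + e, with e independent of w and no constant bias. Let s be the between-patient share of axillary variance and c = var(e)/var(w). The covariance between methods is the between-patient variance alone, so

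pooled ICC = s / [s + (1+c)(1−s)/2]

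The documents give neither s nor c, so both are assumed:

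| s | c = 0 (camera flat within patient) | c = 1 (independent noise equal to the within-patient variation) |
|---|---|---|
| 0.50 | 0.50/0.75 = 0.67 | 0.50 |
| 0.60 | 0.60/0.80 = 0.75 | 0.60 |
| 0.667 | 0.667/0.833 = 0.80 | 0.67 |
| 0.80 | 0.80/0.90 = 0.89 | 0.80 |

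Solving for an ICC of 0.80 gives s = 0.8a/(0.2+0.8a) with a = (1+c)/2. That is 0.4/0.6 = 0.67 for c = 0 and 0.8/1.0 = 0.80 for c = 1.

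**3. A tracking camera with the same ICC.** Let the camera be b + w + e, with e independent at each reading and of variance 0.5 times the total axillary variance. The ICC is 1/(1 + 0.5/2) = 0.80. At s = 0.667 its within-patient agreement is 0.333/(0.333 + 0.25) = 0.57. The flat camera in step 2 also has a pooled ICC of 0.80 at s = 0.667, with within-patient agreement of 0. The pooled figure cannot tell these two cameras apart.

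**4. Simulation.** The layout of 25 patients with 9 pairs each is assumed (1,000 runs per setting, absolute-agreement ICC, non-tracking camera with c = 0). At s = 0.667 the mean ICC was 0.78, and 41% of runs reached 0.80. At s = 0.80 the mean was 0.88, and 97% of runs reached 0.80. At s = 0.50 the mean was 0.64, and 0.4% of runs reached 0.80. The within-patient coefficient averaged 0.00 throughout.

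**The case against.** The strongest reply is that the primary objective asks for concordance at the same moments, as a first step, and an agreement ICC over paired readings answers that. The protocol does not say that patient will be ignored, and a separate analysis plan could specify the ICC model. This stands in part. The overall ICC is a legitimate primary measure and should stay. But the protocol's own analysis section names one ICC as the only agreement statistic, and its collection rule fixes the repeated pairs, so the mixing follows from what is written.

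A reader might infer that a camera which follows nothing would be expected to reach 0.80. The documents do not support that. The background gives 35.3 to 37.7°C as variation among individuals or within one person, so it cannot be taken as between-patient spread alone. If that range is read as ±2 SD of the total (SD 0.6°C), with an assumed within-patient SD of 0.3°C and camera noise of the same size, the ICC is (0.36 − 0.09)/0.36 = 0.75. An equal split gives 0.50 to 0.67. A constant camera bias would lower an absolute-agreement ICC further. Zero tracking is a limiting case, used here to show what the statistic cannot separate.

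A reader might also infer that the ICC is unfair to a camera that tracks well but has patient-specific offsets. It is not. With axillary variance 0.45 (0.36 between, 0.09 within) and offset variance 0.36, the ICC is 0.45/0.63 = 0.71. That is a valid finding of poorer agreement, and such offsets would also harm classification at 37.5°C.

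Finally, 0.8 is the expected value in the precision calculation and not a pass mark, and Objectives 3 to 5 are not conditional on the ICC.

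**Conclusion.** The point holds as a limit on what the primary result can show. One ICC over repeated pairs, with no patient term, cannot reveal within-patient tracking. Objectives 4 and 5 mainly need that tracking, and Objective 3 needs it together with the correct level. How far the ICC could mislead depends on an unstated variance split. For an unbiased non-tracking camera it is about 0.50 to 0.67 at a half share between patients, and it reaches 0.80 only at a share of about 0.67 (camera flat within patient) to 0.80 (independent noise equal to the within-patient variation). The 224 pairs are reproduced and are not challenged here. This is a cheap improvement to the analysis. It does not invalidate the primary objective.

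**What to change.** In the Statistical Analysis Plan section, keep the overall ICC as the primary agreement measure, but estimate it from a mixed model on the same pairs with patient as a random effect. The model also needs a term for occasion within patient, so that within-patient variation shared by the two devices can be estimated. Report a within-patient component beside the ICC, for example the repeated-measures correlation or the agreement of deviations from each patient's own mean. State that conclusions about thermal curves rest on the within-patient component, and that conclusions about fever detection rest on both level and tracking.

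The cost is a few sentences and slightly more analysis. Data Collection already provides a code for each patient and a date and time for each camera record, so no new measurements are needed. The one drawback is that patients with a single pair add nothing to the within-patient part.

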Another issue in fever monitoring, especially with sporadic measurements rather than continuous monitoring, is that febrile peaks may go unnoticed or that the maximum or minimum values that the patient will experience may not be captured.

Therefore, as a first step, the main purpose of this study would be to establish the concordance between axillary temperature measurements (widely used method) taken in patients multiple times a day and temperatures recorded by a thermal imaging camera at the same moments.

Thermal imaging cameras have been widely used during the Covid-19 pandemic for fever screening in healthcare settings and other facilities(12). Their use in hospitalized patients could translate into numerous advantages compared to routine clinical practice. Firstly, it is a non-invasive and contactless measurement, reducing the risk of pathogen transmission, especially in patients colonized by multidrug-resistant microorganisms, and facilitating measurement in patients with compromised skin integrity. Secondly, the automated and continuous acquisition of temperature provides valuable information that has proven useful in patient management

without requiring extra effort from healthcare professionals and may even reduce the nursing and auxiliary workload.

However, the lack of diagnostic test validity studies for most thermal imaging cameras and contradictory results found in published studies (13) have led to their limited use in the hospital environment. Despite this, recent systematic reviews emphasize their great potential pending further studies to validate their utility (14, 15). Therefore, within one of the secondary objectives of this study, we also aim to assess the validity of these cameras as a diagnostic test for fever and hypothermia.

In this regard, the use of thermal imaging cameras integrated into a system capable of automated and real-time peripheral temperature acquisition could potentially lead to a change in the standard practice for temperature monitoring in ICUs. Additionally, this system would provide a wealth of data that could be used to train intelligent systems through machine learning algorithms in the near future, with the goal of predicting events such as the onset of fever, nosocomial infections, or shock.

Hypothesis and Objectives

Hypothesis:

Temperature measurements using thermal imaging cameras in critical patients show good concordance with those taken using contact thermometers in the axilla.

Objectives:

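### The primary agreement result is an intraclass correlation alone; no paired difference, limits of agreement or acceptable error in °C is planned

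*Protocol*

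**What the plan says.** The primary objective is the concordance of camera temperature with axillary temperature. The hypothesis is that camera measurements "show good concordance with those taken using contact thermometers in the axilla".

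The protocol's Statistical Analysis Plan section gives one statistic for this: agreement "will be assessed, as these are quantitative variables, through the intraclass correlation coefficient". It does not say whether the coefficient measures consistency or absolute agreement. The Sample Size section asks for 224 pairs to estimate an intraclass "Correlation Coefficient (expected to be 0.8 or higher) with an estimation error of +- 0.05 points", with 95% confidence and 10% loss.

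Other text that bears on the point:

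- **Descriptive rule (Statistical Analysis Plan).** Quantitative variables are summarised by mean and SD if normal, "or if not normally distributed, using median and interquartile range".
- **Diagnostic accuracy (Statistical Analysis Plan).** Sensitivity, specificity and predictive values are planned for fever (axillary 37.5°C or above) and hypothermia (axillary below 34.2°C), as a secondary objective.
- **Measurement (Standard Practice in Peripheral Temperature Measurement in Our Unit).** "Axillary temperature measurement through standard practice will be repeated every 8 hours", and readings are "collected in triplicate to establish an average used for assessing concordance at that point". The 15% rule in that section compares the axillary replicates with each other, not the two methods.
- **Camera reading (Adequacy of Regional Thermal Measurement).** The camera scans the whole image to "extract the point of maximum temperature found". "A direct visual check of a sample of thermal images will be performed by the researchers", and all images are to be classified automatically by heat source.

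**The concern.** An ICC is the share of total variance that is due to true differences between the temperatures measured. It therefore rises when the sample is more varied, even if the camera's error is unchanged. It has no unit, so it does not tell a unit how far a camera reading may lie from the axillary value. One value can also come from an offset that recalibration would remove or from scatter that it would not.

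An upward offset is plausible here, because the camera reports the hottest point in the image and the protocol itself names staff and devices as possible false sources. Images are to be checked, but the protocol does not say that misattributed readings leave the concordance analysis.

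At stake is whether the main result answers the study's question in °C. The hypothesis of good concordance has no criterion on the temperature scale, and the ICC of 0.8 is a planning value, not a stated criterion.

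**Working it through.** **1. The plan's own figure.** Inputs from Sample Size: ICC ρ = 0.8, half-width 0.05 (full width w = 0.10), 95% confidence (z = 1.96), 10% loss; k = 2 values per pair. Bonett's precision formula:

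n = 8z²(1−ρ)²(1+(k−1)ρ)² / [k(k−1)w²] + 1 = 8 × 3.8415 × 0.04 × 3.24 / (2 × 0.01) + 1 = 199.14 + 1, rounded up to 201.

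201/0.9 = 223.3, rounded up to 224. The stated 224 is reproduced and is not in dispute.

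**2. What an ICC of 0.80 means in °C.** The protocol gives no SD. Its background section quotes a normal range of 35.3 to 37.7°C. Read as ±2 SD (an assumption), the total SD is s = 2.4/4 = 0.6°C. ICU patients may vary more, so 0.8 and 1.0°C are also used. With no offset and equal variances for the two methods (assumed):

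SD of differences = s × √(2 × (1 − 0.80)); limits = ±1.96 × SD of differences.

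- s = 0.6: SD of differences 0.379, limits ±0.74°C.
- s = 0.8: SD of differences 0.506, limits ±0.99°C.

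**3. Same error, different spread.** Hold the SD of differences at 0.379 (limits ±0.74°C). ICC = 1 − (0.379²/2)/s² gives 0.80, 0.89 and 0.93 at s = 0.6, 0.8 and 1.0°C.

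**4. Same ICC, different kind of error.** Absolute-agreement ICC = vt/(vt + ve + d²/2), where vt is the true variance, ve the error variance per method and d the offset. Limits are d ± 1.96√(2ve). Take vt = 0.512.

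- ve = 0.128, d = 0: ICC = 0.512/0.640 = 0.80, limits ±0.99°C.
- ve = 0.048, d = 0.4: ICC = 0.512/(0.512 + 0.048 + 0.080) = 0.80, limits −0.21 to +1.01°C.

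The within-method variance is 0.64 in the first case and 0.56 in the second.

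**5. Whether the limits can be recovered from the reported summaries.** Suppose the two means differ by 0.4°C, each method has SD 0.8°C (variance 0.64) and the ICC is 0.80.

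- Consistency form: ve = 0.2 × 0.64 = 0.128, SD of differences 0.506, limits −0.59 to +1.39°C.
- Absolute-agreement form: vt = 0.8 × (0.64 + 0.08) = 0.576, ve = 0.064, SD of differences 0.358, limits −0.30 to +1.10°C.

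With the form unnamed, the limits cannot be worked back.

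**6. Precision of the added results.** Pairs after loss: 224 × 0.9 = 201.6, about 202. For SD of differences 0.379 to 0.506, with pairs treated as independent, the 95% half-widths are:

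- Mean difference: 1.96 × SD/√202 = 0.05 to 0.07°C.
- Each limit: 1.96 × SD × √(1/202 + 1.96²/(2 × 201)) = 0.09 to 0.12°C.

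Now assume 40 patients with 5 pairs each and half of the difference variance between patients. The variance of the mean is multiplied by 1 + 4 × 0.5 = 3.

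- Mean difference: 1.96 × SD × √(3/200) = 0.09 to 0.12°C.
- Each limit, from variance components: the total variance (in units of SD²) is estimated as MSB/5 + 0.8 × MSW, with expected mean squares 3 and 0.5 on 39 and 160 degrees of freedom. Its variance is (1/25)(2 × 9/39) + 0.64(2 × 0.25/160) = 0.0205, so the variance of the estimated SD is 0.0205/4 = 0.0051. The half-width is 1.96 × SD × √(0.015 + 1.96² × 0.0051) = 0.14 to 0.18°C.

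Simulation of the clustered case gives the same values.

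**The case against.** The strongest reply is one of scope. A separate SAP may exist, and the ICC form, confidence intervals and the handling of repeated pairs are often left to it. The objective, sample size and analysis all use the same recognised statistic, and nothing is misstated. This has some force for the ICC form and for clustering. It has less for the main point, because the protocol itself chooses the primary method, in a section headed Statistical Analysis Plan, and sizes the study on it.

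Second, the diagnostic-accuracy analysis is a partial check. If the camera is read at the same cut-offs, a marked upward offset would tend to lower specificity for fever and sensitivity for hypothermia. That is fair, but it gives no error in °C. The descriptive rule may likewise expose a crude offset, through either means or medians. It gives no paired difference, confidence interval or limits.

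Third, describing the aim as degree of agreement suggests the absolute-agreement form. If that is meant, the consistency branch of step 5 falls away, but steps 2 to 4 are unaffected.

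Fourth, the study calls itself a first step and no replacement decision is planned on it. This limits the harm. It does not remove the need to know the error in °C, since the protocol presents the camera as a possible change to standard monitoring.

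Finally, the magnitudes rest on assumed SDs and offsets. That is correct: they show how the ICC behaves and do not predict this study's result.

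**Conclusion.** The concern holds. Followed as written, the primary analysis gives a ratio that depends on the sample's temperature spread and does not state the camera's error. Under the assumed total SDs of 0.6 and 0.8°C, the expected ICC of 0.80 is compatible with limits of about ±0.74 and ±0.99°C. An unchanged error can appear as an ICC anywhere from 0.80 to 0.93 as the spread goes from 0.6 to 1.0°C. These figures also assume equal error variance for the camera and the axillary mean, and no offset unless one is stated. The ICC is not wrong in itself and the sample size is sound; what is missing is the result on the temperature scale. The change should be made, though the data would remain usable without it.

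**What to change.** In the protocol's Statistical Analysis Plan section:

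1. Keep the ICC, and name it as absolute agreement between the camera value and the mean of the triplicate axillary readings.
2. Report as co-primary results the mean camera-minus-axilla difference and the 95% limits of agreement in °C, each with a 95% confidence interval. Use a Bland-Altman analysis that allows for several pairs per patient.
3. State, before the data are seen, the difference in °C that the investigators will accept as good concordance.

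The cost is a few sentences and a little more analysis of pairs already being collected. The 224 pairs do not change, and step 6 shows that they give usable precision even with fairly strong clustering. The one drawback for the study team is that the conclusion may look less favourable than an ICC alone.
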